## 7.6 Obtaining Adverse Event Information

At every study visit, patients will be asked a standard non-leading question to obtain any medically related changes in their wellbeing. In addition to patient or Investigator observations, AEs as defined in section 7.0 and 7.2 will be documented from any data collected (e.g., laboratory values, physical examination findings), or other documents that are relevant to patient safety.

## 7.7 Assessment of Causality

The Investigator's assessment of an AE's relationship to treatment is part of the documentation process, but it is not a factor in determining what is or is not reported in the study. If there is any doubt as to whether a clinical observation is an AE, the event should be reported.

The relationship or association of the test article in causing or contributing to the AE will be characterized using the following classification and criteria:

- **Unrelated:** This relationship suggests that there is no association between the surgery and the reported event.
- **Possible:** This relationship suggests that treatment caused or contributed to the AE, i.e. the event follows a reasonable temporal sequence from the time of surgery and/or follows a known response pattern to the surgery, but could also have been produced by other factors.
- **Probable:** This relationship suggests that a reasonable temporal sequence of the event with drug administration exists and the likely association of the event with the surgery. This will be based upon the known or previously reported complications to the surgery, or judgment based on the Investigator's clinical experience.
- **Definite:** This relationship suggests that a definite causal relationship exists between the surgery and the AE, and other conditions (concurrent illness, progression/expression of disease state, or concurrent medication reaction) do not appear to explain the event.

## 7.8 Assessment of Severity

Adverse Event severity will be rated by the Investigator as mild, moderate, or severe using the National Cancer Institute Common Terminology Criteria for Adverse Events version 4.0.

Changes in the severity of an AE should be documented to allow an assessment of the duration of the event at each level of intensity to be performed. Adverse events

characterized as intermittent require documentation of onset and duration of each episode.

## **8.0 PATIENT WITHDRAWAL**

Patients will be advised that they may voluntarily withdraw from the study at anytime, for any reason and it will not affect their medical care. However, in such cases, appropriate effort will be made by the Investigator to determine the reason for voluntary withdrawal from the study and to document reason for withdrawal in the medical record, if known.

The last known status of these patients will be reported with the study results and all attempts to locate patients lost to follow up will also be documented.

Patients will be informed that, should they withdraw from the study, they should remain under the care of an appropriately experienced physician until the physician deems further follow-up unnecessary.

The following are circumstances for which a patient would be identified as not continuing her participation in the study:

- Study Completed / Terminated
- Death
- Voluntary Withdrawal
- Unable to Return
- Physician discretion
- No recurrence of cervical cancer at 5 years after completion of initial chemoradiation therapy
- Failure to complete treatment due to toxicity

If a patient relocates to another geographic area, which requires a change of physician, reasonable attempts will be made to locate and request cooperation from that physician in order to complete follow-up.

In many instances patient withdrawal from the study constitutes a cessation of treatment. In these cases, permission should be obtained from patients by study staff to continue monitoring their disease state (relapse, survival, toxicity etc) via patient records as this is a crucial component of the study for which consent was originally obtained.

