If the paraaortic nodes for patients with positive common iliacs are treated, then PTV must end at the top of L2; for patients with positive paraaortic nodes, the PTV must end at the top of T12 (therefore, the CTV must end several slices below these endpoints). The top of the field should be at least one vertebra above the highest positive node. Bowel – will be outlined on every slice, including up to 2 cm above the planning target volume and no more. It includes the volume surrounding loops of small bowel out to the edge of the peritoneum because the bowel may lie within this space at any time throughout the course of treatment.

The dose constraints for critical structures are as follows:

- Bowel:  $\leq 30\%$  to receive  $> 40$  Gy
- Rectum:  $\leq 60\%$  to receive  $> 45$  Gy
- Bladder:  $\leq 35\%$  to receive  $> 45$  Gy
- Kidneys: 2/3 of each kidney to receive  $\leq 18$  Gy
- Spinal cord: no more than 45 Gy at any point with a volume of 0.03 cc or greater

*Follow-Up/Surveillance:*

A PET scan will be obtained at 3 months after completion of chemoradiation therapy. CT scans will be obtained every 6 months for the next three years thereafter. Follow-up surveillance of patients will consist of serial clinical examinations by an oncologist every 3 months for the first 2 years, every 6 months for the next 3 years and annually thereafter. Patients will come off study at 5 years after completion of initial chemoradiation therapy or at time of death.

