### Analysis

We will use descriptive statistics to summarize patient demographic and clinical characteristics by treatment group.

We will estimate overall survival (OS) with the product limit estimator of Kaplan and Meier [19], and we will estimate the 3-year OS with a 95% confidence interval. We will also estimate the median OS with a 95% confidence interval. We will use the log-rank test to compare the 2 treatment groups with respect to OS.

We will also use the log-rank test for the interim analysis of OS, which will take place after 131 deaths have been observed. If the p-value from this test is  $< 0.0031$  the study will be stopped for efficacy, and if the p-value from this test is  $> 0.3217$  the study will be stopped for futility.

We will use Cox [20] proportional hazards regression to model OS as a function of treatment and other well-known and potential prognostic factors such as clinical stage, histology, and grade. We will estimate the hazard ratio for treatment (preoperative paraaortic surgical staging vs not) and other potential prognostic factors with 95% confidence intervals.

We will perform similar analyses for disease-free survival (DFS) as for OS.

We will tabulate the numbers of patients with particular short- and long-term morbidities including intraoperative and postoperative complications and treatment delay for each treatment group, and we will use the chi-square test to compare treatment groups with respect to the incidence of these morbidities.

For the treatment arm with pretreatment paraaortic surgical staging we will estimate the sensitivity of pretreatment radiologic staging examinations to detect metastatic disease with a 95% confidence interval. The findings of the pretreatment paraaortic surgical staging will be considered the true diagnosis of metastatic disease.

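### Section 8 ends study participation for women who cannot complete treatment because of toxicity, so their survival follow-up rests on fresh permission and chart records

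*Combined protocol and SAP*

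**What the plan says.** Section 8.0 opens its list with "The following are circumstances for which a patient would be identified as not continuing her participation in the study". One entry is "Failure to complete treatment due to toxicity"; physician discretion is another. The lead-in concerns participation in the study, not treatment alone.

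Section 4.0, under Follow-Up/Surveillance, says "Patients will come off study at 5 years after completion of initial chemoradiation therapy or at time of death". Toxicity is not mentioned there.

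The closing paragraph of section 8.0 says "In many instances patient withdrawal from the study constitutes a cessation of treatment", and that in those cases "permission should be obtained from patients by study staff to continue monitoring their disease state (relapse, survival, toxicity etc) via patient records". It calls this monitoring crucial and says that consent for it was given at the outset. Earlier in the section, on voluntary withdrawal, it says "The last known status of these patients will be reported with the study results", and that attempts to trace women lost to follow-up will be documented.

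In section 5.0, the Analysis part says "We will use the log-rank test to compare the 2 treatment groups with respect to OS". It contains no intention-to-treat statement and no rule for censoring OS. The sample size text states no allowance for dropout.

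**The concern.** A woman who stops chemoradiation because of toxicity has not withdrawn consent, and nothing about stopping treatment requires her survival follow-up to end. A site reading section 4.0 would keep her on the visit schedule. A site reading the list in section 8.0 could close her participation and then need her permission to look at her records.

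This matters because the primary endpoint is OS and the analysis is driven by deaths. Women who cannot finish chemoradiation probably have a worse prognosis, so losing them would be informative. Only the experimental arm has the lymphadenectomy and, for node-positive women (about 21% expected from false-negative imaging), extended-field radiation. Exits could therefore be more frequent in that arm, and lost deaths there would flatter surgical staging. Disease-free survival depends on the section 4.0 scans and examinations, which record review does not guarantee. Long-term morbidity is an objective too, and the rule ends participation for the women with treatment-limiting toxicity.

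**Working it through.** **1. The plan's own figure.** Inputs from section 5.0: 3-year OS 61% vs 70%, a maximum of 348 deaths, a look at 174 deaths with efficacy p < 0.0031 and futility p > 0.3217, and final p < 0.049. HR = ln(0.70)/ln(0.61) = 0.7216. Simulating this group-sequential design gives 80.4% power, against the stated 80%. The design reproduces when every patient is followed for survival.

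**2. Assumptions.** The documents give no rate of toxicity-related non-completion in either arm and no prognosis for these women. I assumed:
- exits of 5% or 10% in both arms, or 5% control vs 10% or 15% surgical;
- a death hazard in women who exit of 2 or 3 times that of the others;
- exit at 0.25 years;
- 5-year uniform accrual and analysis at 7.6 years;
- exponential survival within groups, with 3-year OS of 61% in both arms (no treatment effect at 3 years).

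**3. Unequal exits, no true 3-year difference.** Cox HR from 400,000 women per arm, by the share of exits still followed for survival. The Monte Carlo standard error of ln(HR) is about 2/√440,000 = 0.003.

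| Exits, control / surgical | Hazard multiple | All followed | 80% | Half | None |
|---|---|---|---|---|---|
| 5% / 10% | 2 | 1.000 | 0.990 | 0.980 | 0.964 |
| 5% / 10% | 3 | 0.993 | 0.981 | 0.970 | 0.944 |
| 5% / 15% | 2 | 0.992 | 0.985 | 0.965 | 0.933 |
| 5% / 15% | 3 | 0.991 | 0.974 | 0.946 | 0.887 |

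Moving the exit to 0.2 years and the analysis to 8.8 years gives almost the same last column: 0.965, 0.945, 0.931 and 0.892, against 0.997, 0.993, 0.992 and 0.982 with full follow-up. With no follow-up, 3-year OS is overstated by 1 to 2 points in the control arm and 2 to 5 points in the surgical arm.

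**4. Where there is no HR bias.**
- Equal exits of 5% or 10%, 2 to 3 times the hazard, all lost: the null HR is 1.00, and the HR under the design effect is 0.71 to 0.72. Under that effect, deaths at 7.6 years fall from about 301 to 253–281, and 3-year OS is about 1 to 3 points too high in both arms.
- Unequal exits with the same death hazard as other women: the HR stays at about 0.72.

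HR bias therefore needs unequal rates, a different prognosis and loss of survival follow-up all together.

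**5. False-positive rate.** Take the ratio of the HR with no follow-up to the HR with full follow-up, from the 8.8-year runs: 0.965/0.997 = 0.968 at the mild end and 0.892/0.982 = 0.908 at the severe end. For a single final test at two-sided 0.049 (z = 1.969) with 348 deaths, the one-sided chance of a false benefit is 1 − Φ(1.969 + ln(ratio) × √(348/4)):
- no bias: 1 − Φ(1.969) = 2.45%;
- ratio 0.968: 1 − Φ(1.969 − 0.303) = 4.8%;
- ratio 0.908: 1 − Φ(1.969 − 0.900) = 14.3%.

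These are upper figures, because they ignore the interim futility rule. With that rule and a look at 174 deaths, the baseline is 2.05% and the range 4.0% to 12.1%. With the look at 131 deaths, which the Analysis text gives instead, the baseline is 1.8% and the range 3.6% to 10.7%.

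**The case against.** The strongest reply is that section 8.0 already deals with this. Its closing paragraph addresses withdrawals that amount to stopping treatment, which fits stopping for toxicity. It directs staff to keep monitoring survival and treats that as essential. A chart is a usable source for a date of death. Section 4.0 does not say that 5 years and death are the only exits. It omits voluntary withdrawal too, so section 8.0 can be read as a supplement to it.

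Much of this stands. A reader might infer that the plan censors these women, and does so unequally between arms. The documents do not support that reading: no text says they are censored, and no text gives exit rates by arm. The background in section 2.0 points the other way, since it reports that the laparoscopic technique was safe, did not delay chemoradiation and did not appear to add radiotherapy complications. Both arms receive chemoradiation. If the extended field alone caused a 10-point excess of exits, the excess among the roughly 21% who need it would have to be about 10/0.21 = 48 points.

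The reply does not close the gap. The provision is framed around patient withdrawal, asks for permission for monitoring that it says was already consented to, and sets no contact schedule. Reporting last known status describes a loss but does not prevent it. Nothing in section 5.0 determines how these women enter the OS analysis.

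**Conclusion.** The point holds as a risk created by a stated rule that is not reconciled with section 4.0. It does not show that deaths will be discarded or that the comparison is biased.

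Its size depends wholly on assumptions. In the worst case examined (5% vs 15% exits, 3 times the death hazard, nobody followed), an HR near 1 would read about 0.89. The milder unequal cases with complete loss give about 0.93 to 0.96. With 80% followed through records, the HR is 0.97 to 0.99, close to the value with full follow-up. The more robust cost, which needs no imbalance, is lost deaths in an event-driven trial and optimistic 3-year OS estimates. The direction favours surgery only if exits are more common in that arm; the structure of the trial makes this plausible but the documents do not establish it. This is a worthwhile, inexpensive improvement.

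**What to change.** Reconcile section 8.0 with the follow-up text in section 4.0:

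- Record toxicity-related failure to complete treatment as end of protocol treatment only, not end of study. Treat physician discretion the same way for follow-up purposes. This changes no rule on when treatment stops.
- Continue survival and relapse follow-up of every randomised patient under the original consent, on the section 4.0 schedule, unless she withdraws consent to follow-up.
- In the Analysis part of section 5.0, state that OS is compared by randomised arm in all randomised patients, with women not known to have died censored at the date last known alive.
- Report the number of women who stop treatment for toxicity and the completeness of survival follow-up, by arm.

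The cost is a wording amendment, matching consent text, and some added visits or vital-status checks for a small group of women.

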## **9.0 STUDY COMMITTEES**

### **9.1 Trial Safety Committee (TSC)**

An independent Trial Safety Committee (TSC) will be assembled to review the safety and efficacy data collected during the study. They will be composed of individuals who

are independent of the study and are not involved (either directly or indirectly) in the management of this study. The membership includes the following:

- 3 gynecological oncologists who are otherwise not related to the trial;
- 2 Statisticians who are otherwise not related to the trial;
- 1 public member

The TSC will be responsible for monitoring, on an ongoing basis, any of the following events:

- General Toxicity (NCI-CTC AE, v4.0): grade 3 and grade 4 adverse events, serious adverse events
- A patient death (grade 5)

The first safety analysis will be performed after 20 patients have completed treatment. All further TSC reviews should take place twice per year and the committee will review all safety data collected during the study.

Following each meeting, the committee will recommend that the study continues according to the protocol or may suggest changes to the protocol based on the outcome of the data review. In exceptional cases the committee may recommend stopping the study due to safety reasons.

## **9.2 Trial Management Committee (TMC)**

A Trials Management Committee (TMC) will be assembled to review and manage the trial's progress. The TMC will consist of the study chair, the co-chairs, two study coordinators, and the study statistician. The TMC will meet/confer every four months.

Following each meeting, the committee will recommend that the study continues according to the protocol or may suggest changes to the protocol based on the outcome of the data review.

## **10.0 DATA HANDLING AND QUALITY ASSURANCE**

### **10.1 Data Management**

Participating Investigators must agree to maintain adequate case histories for the patients treated as part of the research under this protocol. The Investigator agrees to maintain accurate source documentation as part of the patient's case history.

### **10.2 Data Security**

Access to the study data base will be by username and password and will be restricted to trial personnel.

### **10.3 Data Quality Assurance**

Accurate and reliable data collection will be assured by verification and cross-check of the collected data against the patients' medical record. The data collected will be entered directly onto a secure electronic database with access limited to study personnel. A comprehensive validation check program will verify the data and discrepancy reports will be generated accordingly for resolution by the investigator.

## **11.0 ADMINISTRATIVE CONSIDERATIONS**

The following administrative items are intended to guide the conduct of the trial.

### **11.1 Confidentiality**

All records will be kept in a secure storage area with limited access. Clinical information will not be released without the written permission of the patient or the patient's guardian, except as necessary for monitoring by CDMU or its representative, regulatory authorities, or the IRB.

The Investigator and all employees and co-workers involved with this study shall not disclose or use for any purpose, other than performance of the study, any data, records or other unpublished, confidential information disclosed to those individuals for the purpose of the study.

### **11.2 Modification of the Protocol**

The TMC must review and approve any changes in this research activity. Amendments to the protocol must be submitted in writing to the Investigator's IRB/HREC for approval prior to patients being enrolled into an amended protocol.

### **11.3 Informed Consent**

A written informed consent shall be obtained from each patient prior to the patient's entrance into the study. Before recruitment and enrolment, each prospective patient will be given a full explanation of the study and be allowed to read the approved informed consent form. The Investigator will inform the patient of the purpose of the study, randomization of study groups and the follow-up schedule. The Investigator will discuss foreseeable risks involved, as well as potential benefits that result from the use of the new surgical technique. The Investigator will inform the patient that her medical records will be subject to review by government authorities, members of TSC and by the IRB.

The patients will be informed by the Investigator that they are free to refuse participation in this study and, if they choose to participate, that they may withdraw from the study at any time without compromising further medical care.

Once the Investigator is assured that the individual understands the implications of participating in the study, the patient will be asked to give consent to participate in the study by signing the informed consent form. The Investigator shall provide a copy of the signed informed consent to the patient.

#### **11.4 Protocol Violations and Deviations**

The Investigator or designee should document and explain any deviation from the approved protocol. The Investigator may deviate from the protocol to eliminate an immediate hazard to trial patients without prior IRB approval. As soon as possible after such an occurrence, the Investigator should submit the implemented deviation or change, the reasons for it to the site IRB to CDMU, if required.

A deviation from the protocol is an unintended and/or unanticipated departure from the procedures and/or processes approved by the IRB and agreed to by the Investigator. Deviations usually impact individual patients or a small group of patients and do not involve inclusion/exclusion or primary endpoint criteria.

A protocol violation occurs when there is non-adherence to the protocol that results in a significant added risk to the patient, when the patient or Investigator has failed to adhere to major protocol requirements, or when there is non-adherence to regulatory authorities' regulations and/or ICH Good Clinical Practice (GCP) guidelines.

CDMU or its representative will review the protocol violations and deviations during the monitoring visit and will notify the Investigator of violations and deviations verbally or in writing of their findings. The Investigator should notify the IRB/HREC of protocol violations and deviations in accordance with the IRB requirements.

## **12.0 STUDY CONDUCT**

The study will be conducted according to the principles of the ICH E6 Guideline on GCP and the principles of the World Medical Association Declaration of Helsinki. The Investigator will conduct all aspects of this study in accordance with all national, state, and local laws of the pertinent regulatory authorities.

